9.4. Planned Interim Analysis

We will utilize the UW ICTR Data Monitoring Committee (DMC) to oversee the study and is described further in section 11.6. Source documents may be reviewed to allow the DMC to independently judge whether the overall integrity and conduct of the protocol remain acceptable based on data provided and reported by the Principal Investigator. The DMC will make recommendations to the Principal investigator that could include actions of continuation, modification, suspension or termination.

10. Data Collection, Handling and Record Keeping

10.1. Data Confidentiality

Only PI and study team members will have access to the subject research records and the data entered in both the OnCore and REDCap systems. Data will not be shared with any other researchers outside of the study team. No personal identifiable information will be released to the third parties. Only summary of the data generated will be provided to the industry.

10.1.1. Confidentiality of Subject Records

By signing the protocol, the Investigator agrees that the, IRB, or Regulatory Agency representative may consult and/or copy study documents to verify case report form (CRF) data. By signing the consent form, the subject agrees to this process. If study documents will be photocopied during the process of verifying CRF information, the subject will be identified by unique code only and full names and similar identifying information (such as medical record number or social security number) will be masked.

The Clinical Site Investigators will ensure that the identity of subjects will be protected. All study records will be maintained in a secure fashion with access limited to essential study personnel only. The Clinical Site Investigators will maintain an enrollment log that includes subject identifying information and links subjects to their study-specific identification number. This information will also be available in the ICTR OnCore and REDCap systems.

10.2. Data Capture

10.2.1. Source Documents

A majority of the study data will be captured through the electronic medical record (EMR) and Transplant Database. **The data source for the Transplant Database are Transplant Data Mart and Organ and Tissue Donation Database.** Data records include: hospital records, clinical and office charts, laboratory notes, memoranda, subjects' diaries or evaluation checklists, pharmacy dispensing records, recorded data from automated instruments, transcriptions,

microfiches, photographic negatives, microfilm or magnetic media, x-rays, subject files, and records kept at the pharmacy, at the laboratories, and at medico-technical departments involved in the clinical trial.

10.2.2. Case Report Forms

The study CRF is a data-reporting instrument for the study. All data requested on the CRF will be recorded. All missing data will be explained. All entries will be printed legibly in black ink. If any entry error has been made, to correct such an error, a single straight line will be drawn through the incorrect entry and the correct data will be entered above it. All such changes will be initialed and dated.

10.2.3. Electronic Case Report Forms (eCRFs)

Some of the data that will be exported for analysis will not be captured on paper CRFs, rather directly entered into the ICTR OnCore or ICTR REDCap Data Management System, including but not limited to results of laboratory tests, physical examinations, imaging, etc.

10.2.4. Missing Data

Every attempt will be made to capture all data. If data is missing, additional review of available data from the electronic medical record and/or Transplant Database will be conducted.

10.2.5. Data Collection Tools

Online Collaborative Research Environment (OnCore) will serve as the Clinical Trial Management System for this study. ICTR OnCore is supported by the UW School of Medicine and Public Health Information Technology (SMPH-IT) staff and managed by UW ICTR.

OnCore is a sophisticated, web-based data management system that: a) ensures secure, easy data entry at multiple sites; b) integrates multiple data sources; c) provides controlled, secure access to sensitive data using role-based access control; d) provides workflow automation; and e) allows export and reporting of data for Data and Safety Monitoring Boards and biostatisticians. This software provides protocol management functions (e.g. subject scheduling; screening, data organization), maintains updated forms, addresses budget development, billing, and fiscal management, generates summary reports, and provides essential links with other research administration and electronic medical records systems. ICTR OnCore eases the burden of the individual researcher and unifies protocol management within research programs and across research sites, enhancing protocol integrity and regulatory compliance efforts.

Data extracted from the EMR will be entered into the REDCap system managed by ICTR. This data will be combined with the data exported from the OnCore system and imported into the same project, allowing REDCap to serve as the final data repository for this study.

10.3. Data Management

The PI is responsible for implementing and maintaining quality control and quality assurance procedures to ensure that trial is conducted and data are generated, documented, and reported in compliance with the protocol, accepted standards of Good Clinical Practice (International Conference on Harmonization E6), and all applicable federal, state, provincial, and local laws, rules, and regulations relating to the conduct of the clinical trial in an ongoing and auditable manner.

10.4. Records Retention

Study records will be retained for a minimum of 7 years after study completion per the UW Madison policy and IRB guidance: <https://kb.wisc.edu/sbsedirbs/page.php?id=42378>. These documents should be retained for a longer period if required by an agreement with the sponsor. In such an instance, it is the responsibility of the sponsor to inform the investigator/institution as to when these documents no longer need to be retained.

11. Assessment of Safety

The investigator is responsible for monitoring the safety of subjects who have enrolled in the study. For this study, adverse events will be solicited from subjects to identify an occurrence or worsening of an unintended sign or symptom,

related to the ingestion of the study drug as per standard of care. The clinical team will ask subjects in each visit if they experienced any new medical related signs or symptoms since taking the study drug. Subjects will be asked about any adverse events they may have experienced. Only the adverse events considered related (possibly, probably or definitely) to the ingestion of the study drug will be entered into and managed in the data management system.

11.1. Specifications of Safety Parameters

The risks to subjects in this trial will be minimized by compliance with eligibility criteria, clinical monitoring, adherence to protocol contraception requirements and investigator guidance regarding specific safety areas. The specific safety areas that will be closely monitored in this subject population are; thrombocytopenia, diarrhea, fatigue, nausea, vomiting, rash, risk of reactivation of viral infection, neutropenia, fluid deficit, uncontrolled hypertension, posterior reversible encephalopathy syndrome (PRES).

11.1.1. Definition of Adverse Events (AE)

Adverse event (AE) means any untoward medical occurrence in a patient or subject administered a pharmaceutical product; the untoward medical occurrence does not necessarily have a causal relationship with this treatment. An AE can therefore be any unfavorable and unintended sign, symptom, or disease temporally associated with the use of a medicinal (investigational) product whether or not it is related to the medicinal product. This includes any newly occurring event, or a previous condition that has increased in severity or frequency since the administration of study drug. AEs will be assessed at study visits and during the final follow-up study visit. Only the adverse events considered related (possibly, probably or definitely) to the ingestion of the study drug will be entered into and managed in the data management system

For the purposes of this study, baseline symptoms will be collected prior to the administration of study intervention. Only those symptoms identified as new or worsened compared to the baseline assessment will be recorded as an AE. In addition, only those abnormal laboratory values or physical examination assessments that are considered clinically significant will be recorded in the study documents. [Pain and hematoma at transplant incision site will not be considered an AE.](#)

11.1.2. Definition of Serious Adverse Events (SAE)

An AE or suspected adverse reaction is considered "serious" if, in the view of either the investigator or sponsor, it results in any of the following outcomes:

- Death
- Life-threatening adverse event*
- Inpatient hospitalization or prolongation of existing hospitalization
 - Subjects must be admitted to an inpatient unit to be eligible for the study, thus the initial hospitalization will not be considered an SAE in and of itself, rather it will only be considered an SAE if the subject is discharged and then re-admitted.
- A congenital anomaly/birth defect
- Persistent or significant disability or incapacity or substantial disruption of the ability to conduct normal life function
- Important medical events that, may not result in death, be life-threatening, or require hospitalization may be considered when, based upon appropriate medical judgement, they may jeopardize the patient or subject and may require medical or surgical intervention to prevent one of the outcomes listed in this definition

*Life-threatening adverse event: An adverse event is considered "life-threatening" if, in the view of the investigator, its occurrence places the subject at immediate risk of death. It does not include an adverse event which, had it occurred in a more severe form, might have caused death.

11.1.3. Definition of Unanticipated Problems (UP)

OHRP considers unanticipated problems involving risks to participants or others to include, in general, any incident, experience, or outcome that meets all of the following criteria:

- Unexpected in terms of nature, severity, or frequency given (a) the research procedures that are described in the protocol-related documents, such as the IRB-approved research protocol and informed consent document; and (b) the characteristics of the participant population being studied;
- Related or possibly related to participation in the research (“possibly related” means there is a reasonable possibility that the incident, experience, or outcome may have been caused by the procedures involved in the research); and
- Suggests that the research places participants or others at a greater risk of harm (including physical, psychological, economic, or social harm) than was previously known or recognized.

The following changes or actions will be considered in response to an UP:

- Modification of inclusion or exclusion criteria to mitigate the newly identified risks
- Implementation of additional safety monitoring procedures
- Suspension of enrollment of new participants or halting of study procedures for enrolled participants
- Modification of informed consent documents to include a description of newly recognized risks
- Provision of additional information about newly recognized risks to previously enrolled participants.

11.2. Classification of an Adverse Event

11.2.1. Severity of Event

All AEs will be assessed by the clinician using the Common Terminology Criteria for Adverse Events (CTCAE) Version 4, each event searchable using the Safety Profiler website (<https://safetyprofiler-ctep.nci.nih.gov/CTC/CTC.aspx>). For AEs not included in the protocol defined grading system, the following guidelines will be used to describe severity.

- **Mild** – Events require minimal or no treatment and do not interfere with the participant’s daily activities.
- **Moderate** – Events result in a low level of inconvenience or concern with the therapeutic measures. Moderate events may cause some interference with functioning.
- **Severe** – Events interrupt a participant’s usual daily activity and may require systemic drug therapy or other treatment. Severe events are usually potentially life-threatening or incapacitating.

11.2.2. Relationship to Study Agent

In a clinical trial, the study product must always be suspect. To help assess, the following guidelines are used.

For all collected AEs, the clinician who examines and evaluates the participant will determine the AE’s causality based on temporal relationship and his/her clinical judgment. The degree of certainty about causality will be graded using the categories below.

- **Definitely Related** – There is clear evidence to suggest a causal relationship, and other possible contributing factors can be ruled out. The clinical event, including an abnormal laboratory test result, occurs in a plausible time relationship to drug administration and cannot be explained by concurrent disease or other drugs or chemicals. The response to withdrawal of the drug (de-challenge) should be clinically plausible. The event must be pharmacologically or phenomenologically definitive, with use of a satisfactory re-challenge procedure if necessary.
- **Probably Related** – There is evidence to suggest a causal relationship, and the influence of other factors is unlikely. The clinical event, including an abnormal laboratory test result, occurs within a reasonable time after administration of the drug, is unlikely to be attributed to concurrent disease or other drugs or chemicals, and

follows a clinically reasonable response on withdrawal (de-challenge). Re-challenge information is not required to fulfill this definition.

- **Possibly Related** – There is some evidence to suggest a causal relationship (e.g., the event occurred within a reasonable time after administration of the trial medication). However, other factors may have contributed to the event (e.g., the participant's clinical condition, other concomitant events). Although an AE may rate only as "possibly related" soon after discovery, it can be flagged as requiring more information and later be upgraded to "probably related" or "definitely related," as appropriate.
- **Unlikely to be related** – A clinical event, including an abnormal laboratory test result, whose temporal relationship to drug administration makes a causal relationship improbable (e.g., the event did not occur within a reasonable time after administration of the trial medication) and in which other drugs or chemicals or underlying disease provides plausible explanations (e.g., the participant's clinical condition, other concomitant treatments).
- **Not Related** – The AE is completely independent of study drug administration, and/or evidence exists that the event is definitely related to another etiology. There must be an alternative, definitive etiology documented by the clinician.

11.2.3. Expectedness

PI will be responsible for determining whether an AE is expected or unexpected. An AE will be considered unexpected if the nature, severity, or frequency of the event is not consistent with the risk information previously described for the study agent in the clinical protocol, the package insert(s), the IRB application or the informed consent document.

11.3. Time period and frequency for event assessment and follow-up

The occurrence of an AE or SAE may come to the attention of study personnel during study visits and interviews of a study participant presenting for medical care, or upon review by a study monitor. All AEs including local and systemic reactions not meeting the criteria for SAEs will be captured on the appropriate CRF. Information to be collected includes event description, time of onset, clinician's assessment of severity, relationship to study product (assessed only by those with the training and authority to make a diagnosis), and time of resolution/stabilization of the event. All AEs occurring while on study must be documented appropriately regardless of relationship. All AEs will be followed to adequate resolution.

Any medical condition that is present at the time that the participant is screened will be considered as baseline and not reported as an AE. However, if the study participant's condition deteriorates at any time during the study, it will be recorded as an AE. UPs will be recorded in the data collection system throughout the study.

Changes in the severity of an AE will be documented to allow an assessment of the duration of the event at each level of severity to be performed. AEs characterized as intermittent require documentation of onset and duration of each episode.

The PI will record all reportable events with start dates occurring any time after the administration of the study drug and for up to 30 days after the date of the last dose of study drug. At each study visit, the investigator will inquire about the occurrence of AE/SAEs since the last visit. Events will be followed for outcome information until resolution, stabilization, or completion of study participation.

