OnCore	Online Collaborative Research Environment, clinical trial management software
PI	Principal Investigator
QA	Quality Assurance
QC	Quality Control
SAE	Serious Adverse Event
SMS	Study Monitoring Service

[figure not shown]
1. Study Summary

Envarsus XR in Delayed Graft Function (E-DGF)	
Short Title and Precis	Envarsus in DGF (E-DGF)
Protocol Number	2018-0530
ClinicalTrials.gov number	NCT03864926
Phase	Phase IV
Methodology	Single center, open randomized trial
Study Duration	2.5 years
Study Center(s)	Single Center
Objectives	Envarsus XR is an extended release tacrolimus designed to deliver tacrolimus more consistently, thus avoiding large fluctuations of tacrolimus trough levels with Envarsus XR compared to immediate release tacrolimus. It is expected that patients with DGF on Envarsus XR will have more stable tacrolimus levels and facilitate early recover from DGF compared to immediate release tacrolimus.
Number of Subjects	Total of 100, 50 in each arm
Diagnosis	Kidney transplant recipients with the diagnosis of DGF
Main Inclusion Criteria	New kidney transplant recipients with DGF transplanted at UW hospital
Main Exclusion Criteria	Multi-organs transplant recipients Patients not on or not planned to be on tacrolimus based regimen after transplant Complications requiring allograft nephrectomy
Study Product, Dose, Route, Regimen	Per UW Abdominal Transplant Immunosuppression Management Adult-Inpatient/Ambulatory Clinical Practice Guideline: immediate release tacrolimus (generic) 0.05 to 0.1 mg/kg/day in two-divided dose by mouth will be used in all patients after kidney transplant as the standard of care (SOC). All subject will receive at least one dose of SOC tacrolimus. Extended release Envarsus XR (study drug) 80% of the total daily dose of SOC tacrolimus or close to the available strength of 0.75 mg, 1 mg and 4 mg tablet as a single tablet or combination of two or more tablets of Envarsus XR once a day by mouth will be used in the study arm and SOC immediate release tacrolimus will be continued in the SOC arm.
FDA status of product	IND Exempt Determination
Duration of administration	Until recovery of DGF to a maximum of 3 months
Reference therapy	Immediate release tacrolimus
Statistical Methodology	Data Analysis: Descriptive statistics for the data will be compiled. Any trends for differences between two groups for the composite endpoints will be assessed.

Figure 1: Schematic of Study Design**Flow diagram:**

Prior to enrollment

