8.2. Study Visits

8.2.1. Screening/Baseline

At screening/baseline visit transplant nephrology provider will decide about the need of dialysis or not and based on that information will document patient to have DGF or not. In that visit, we will review the patient's medical records. Patient will also be informed about the study and their interest will be gauged. If they are interested, then research coordinator will be informed about the potential subject.

Table 2. Medical chart review of standard of care visits

Visit*	Window	Data collection from medical record and Transplant Database
Day 1 contact	+/- 1 days	H&P, brief updates about research project
Day 3	+/- 0 days	H&P, decision for dialysis, decision to adjust study or SOC dose
Day 5	+/- 0 days	H&P, decision for dialysis, decision to adjust study or SOC dose
Day 7	+/- 0 days	H&P, decision for dialysis, decision to adjust study or SOC dose
Additional visits every 2-3 days until DGF recovery	+/- 0 days	H&P, decision for dialysis, decision to adjust study or SOC dose
Monthly up through Month 3 post diagnosis of DGF	+/- 30 days	H&P, decision for dialysis, decision to adjust study or SOC dose

*visits could be more or less depending upon the timing of DGF recovery for maximum of 3 months post-transplant.

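### AE recording opens and closes on dosing with the study drug, a term the protocol uses for Envarsus XR, and the AE baseline is set two ways, so the two arms lack a clearly common safety window

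*Combined protocol and SAP*

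**What the plan says.** **Window.** Under section 11.3 the principal investigator is to "record all reportable events with start dates occurring any time after the administration of the study drug". The closing point uses the same anchor: recording continues "for up to 30 days after the date of the last dose of study drug". Randomisation is not mentioned. The same section also says: "All AEs occurring while on study must be documented appropriately regardless of relationship". That sentence is tied to no dose.

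**Meaning of the term.** The Study Summary (section 1) attaches the label study drug to Envarsus XR. Sections 6.7.2 and 6.7.3 contrast study drug with SOC tacrolimus. In section 8.1, Table 1 has a row for study drug administration and Table 2 a separate row for immediate-release tacrolimus administration.

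**Baseline.** Section 11.3 treats any condition "present at the time that the participant is screened will be considered as baseline and not reported as an AE". Section 11.1.1 says "baseline symptoms will be collected prior to the administration of study intervention", and counts only symptoms that are new or worse than at that assessment.

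**Prior exposure.** The Study Summary states: "All subject will receive at least one dose of SOC tacrolimus". Envarsus XR is then dosed as a conversion from it. Figure 1 puts baseline assessments at Visit 1 and randomisation at Visit 2.

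**What reaches the database.** The opening of section 11 and sections 11.1.1, 11.4.1 and 12.1 admit to the data management system only events judged related to taking the study drug.

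**The concern.** A by-arm safety comparison needs the same recording rule in each arm: the same time zero, the same end and the same baseline. Here the start and end hang on a term that elsewhere names one arm's product. The other arm's product is a drug that patients may already be taking when they are randomised.

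The safety endpoints in section 5.1.3 include infections, tremors, gastrointestinal symptoms, uncontrolled hypertension and electrolyte abnormalities. Events of this kind can plausibly arise in the first days after a transplant, so a shift of a few days in the starting point could move events into or out of one arm. The trial is open-label (section 7.4), which is a further reason to leave little discretion over what counts. The data monitoring committee's adverse event summary (section 11.6) draws on the same records.

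**Working it through.** No figure in the plan tests this point, so the first three steps compare text and the fourth is an illustration.

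**Step 1. Apply the 11.3 window under each reading.**

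| Reading of study drug | SOC arm | Envarsus XR arm |
|---|---|---|
| Envarsus XR only (sections 1, 6.7.2, 6.7.3) | no start, no end | first Envarsus XR dose to 30 days after the last |
| Assigned drug | first immediate-release dose, which may precede randomisation, to 30 days after the last | first Envarsus XR dose, necessarily after randomisation, to 30 days after the last |

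Neither row gives both arms the same starting rule. The end is also loose on the assigned-drug reading. Section 8.2.3 lets patients continue study medication or switch to SOC after leaving the study, so the last dose may fall well beyond study participation.

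**Step 2. Compare the baselines.** The screening rule in 11.3 is identical for both arms. The rule in 11.1.1 depends on when the study intervention begins, and the protocol does not say when that is for a patient who simply continues immediate-release tacrolimus. Take a tremor that begins between screening and the first Envarsus XR dose. Under 11.3 it is not baseline and it precedes the dose-based window. Under 11.1.1 it is baseline. Under the on-study sentence in 11.3 it must be documented. These rules give different answers for one event.

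**Step 3. Does the on-study sentence settle it?** Only partly. It points to a common window, but four other places restrict database entry to events related to the study drug. If that means Envarsus XR, SOC events have no route into the system that section 11.4.1 makes available to the study team, the data monitoring committee and the study monitors.

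**Step 4. Illustrate the size on the assigned-drug reading.** Inputs:

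- mean DGF duration 13.9 days (section 9.1);
- a dialysis-free period of 7 days before a patient leaves the study (sections 6 and 8.2.3);
- the 30-day tail (section 11.3);
- L, the days on tacrolimus before randomisation. This is an assumption, taken up to 7 because screening falls within the first week after transplant (section 6.4.1).

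Reference window = 13.9 + 7 + 30 = 50.9 days, assuming the last on-study dose comes at the end of the dialysis-free week. Relative excess in SOC = L / 50.9:

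- L = 0: 0%
- L = 3: 3 / 50.9 = 6%
- L = 7: 7 / 50.9 = 14%

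If the last dose came at the last dialysis, the window would be 13.9 + 30 = 43.9 days and L = 7 would give 7 / 43.9 = 16%. Extra days are not the same as extra events. Conditions still present at screening are excluded in both arms, so only events that had resolved by screening, or that began between screening and randomisation, could add to the SOC count.

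**The case against.** The strongest reply is that this is loose wording and that a sensible site would use a common start. Table 1 marks study drug administration at Baseline (Day 1) without separating the arms, and it has a dose-adjustment row covering both products. The first exclusion criterion speaks of study drugs in the plural. The on-study sentence applies to everyone, and the screening baseline in 11.3 is the same for both arms. All of this stands: a common start is possible under the text. But the text does not require it, and the related-events restriction works against it.

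Several stronger inferences are tempting and are not supported.

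- *The plan gives the arms different baselines and starting points.* It does not prescribe this. It is a possible result of undefined wording.
- *The SOC window is a third longer.* That comes from 7 / 20.9 = 33%, which leaves out the 30-day tail and ignores the exclusion of conditions present at screening.
- *The bias favours Envarsus XR.* That follows only on the assigned-drug reading. On the Envarsus-only reading it is SOC events that are lost.
- *Some events can be neither baseline nor recordable.* That is true of 11.3's dose-based rule taken alone, but 11.1.1 would make such an event baseline and the on-study sentence would capture it.
- *The one-day tolerance on Day 1 lets the baseline follow the first dose.* That tolerance belongs to a chart-review contact described as "H&P, brief updates about research project". Figure 1 places the baseline assessment before randomisation.
- *Every patient is on tacrolimus by randomisation.* Figure 1 and the inclusion criteria admit patients who are only planned to start. Prior exposure is assured only before the first Envarsus XR dose.

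**Conclusion.** The concern holds as a defect of definition. The start and end of AE recording rest on a term that the protocol uses for one arm's product. Two baseline rules conflict, and one of them is undefined for SOC. The sentence that could unify the window conflicts with the restriction on what enters the database. The by-arm safety comparison may therefore rest on unequal recording.

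Neither the size nor the direction can be fixed from the documents. On the assigned-drug reading, an excess of roughly 14% of recording time in SOC is an upper illustration. It assumes 7 days of tacrolimus before randomisation, the mean DGF duration, and a last on-study dose after the dialysis-free week. The effect on event counts would be smaller. On the Envarsus-only reading the SOC window is undefined, so no percentage applies. The duration-of-DGF and dose-adjustment endpoints and the sample size are not touched. The change should be made, because it is nearly free and removes the ambiguity from the safety comparison.

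**What to change.** - In 11.1.1 and 11.3, start AE recording at randomisation in both arms.
- Define the end as 30 days after the last dose of assigned treatment on study, naming both products (Envarsus XR or immediate-release tacrolimus).
- Use one baseline, recorded at the existing Visit 1 assessment before randomisation. Reconcile the screening rule in 11.3 with it, and add a baseline-symptom row to Table 1 in section 8.1, since neither procedure table there has one.
- Make the same change of term in the opening of section 11 and in sections 11.4.1 and 12.1, so that any relatedness restriction applies equally to both arms. State how that restriction fits with the on-study sentence in 11.3.

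The cost is protocol wording and one table row. No visit is added, because Figure 1 already places baseline assessments before randomisation. There are two downsides. Events before randomisation would be summarised as medical history. A few events between randomisation and the first Envarsus XR dose would count in that arm; recorded onset and dosing dates would allow them to be identified.
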